8.1 Pre-Screening

PrismRA arm:

Prior to Visit 1, potential patient charts may be reviewed to determine eligibility for the study. At the discretion of the Investigator, pre-screening lab tests (i.e., Complete Blood Count (CBC), Clinical Metabolic Panel (CMP), Tuberculosis (TB), and/or C-reactive Protein (CRP)) may be ordered and analyzed per standard of care if the patient has not already received these lab tests within 3 months of the planned study Visit 1.

External control arm:

The entirety of data for each patient (no less than 12 months) prior to the study treatment initiation will be used to assess their medical history and past medication use and to determine their eligibility (see above). For variables required to be up to date at the time of the study treatment initiation, the most recent value within the 3-month period prior to the study treatment initiation will be used, unless otherwise stated (see Table 1, Table 2).

8.2 Screening and Enrollment

PrismRA arm:

At Visit 1, patients will complete the informed consent process. A written, signed informed consent form (ICF) must be obtained prior to the recording or collection of any data under this protocol. Upon signing the ICF, the patient will be considered enrolled into the study.

At the discretion of the Investigator, patients will also be asked to review and sign a medical records release form providing access to their medical records outside of the study. Sponsor or Sponsor designees may access patients' medical records upon study completion for only those patients that provide proper authorization.

Following patient consent, each patient will be assigned a unique study identification number that will be used to track their de-identified data throughout their participation in the study.

External control arm:

Screening/enrollment activities are not applicable for the external control arm of patients identified from real-world data.

8.3 Screen Failures

PrismRA arm:

Screen failures are defined as those patients who consent to participate in the clinical study but did not meet one or more criteria for participation in the study.

External control arm:

Non-initiators of b/tsDMARDs are considered screen failures and will not be in the analysis dataset.

8.4 Summary of Visits and Assessments

[figure not shown]
PrismRA arm:

Data will be collected at Screening/Baseline, Study Treatment Initiation (2–6 weeks after, and then at follow up visits approximately 12 weeks and 24 weeks after Study Treatment Initiation. The allowable time windows are explained in Section 8.5.

External control arm:

Data from clinical encounters over time will be used to provide information for (1) the baseline period (for CDAI assessment), (2) study treatment initiation time point; (3) the 12-week follow-up period; and (4) the 24-week follow-up period. The allowable time windows are explained in Section 8.5.

8.5 Schedule of Visits

PrismRA arm:

The timing for the follow-up visits (visits 3 and 4) should be projected based on the date of Study Treatment Initiation (index date).

External control arm:

The date of study treatment initiation constitutes the index date for the beginning of the follow-up. The 3-month period prior to the index date will be used to ascertain the baseline CDAI. The 12-week follow-up will be defined as the clinical encounter closest to the 12-week time point within the 12 (\pm 4) week visit window. The 24-week follow-up will be defined the visit closest to the 24-week time point within the 24 (\pm 4) week visit window. Depending on feasibility, we will

attempt follow-up windows, such as \pm 6 week window, \pm 3 week window, and \pm 2 week window. Sensitivity analyses with different follow-up windows will be conducted as needed.

8.6 Schedule of Assessments

PrismRA arm:

Procedure	Visit 1 (Screening/ Baseline)	Visit 2 (Study Treatment Initiation) ⁷	Visit 3 (12 Week Follow-up)	Visit 4 (24 Week Follow-up)
Visit Windows	N/A	2-6 weeks	±2 weeks	±2 weeks
Informed Consent	X			
Medical Records Release Form	X			
Eligibility Criteria	X			
RA Medical History	X			
Smoking ⁸				X
Comorbidities ⁸				X
Weight	X		X	X
28 Joint-Count for Tenderness & Swelling	X		X	X
PrismRA ¹	X			
CRP ²	X		X	X
RF ³				
Vectra DA ³				
TB Test ⁴				
Urine Pregnancy Test ⁵				
Physician Global Assessment of Disease Activity	X		X	X
Patient Global Assessment of Pain	X		X	X
Patient Global Assessment of Disease Activity	X		X	X
Health Assessment Questionnaire	X		X	X
RAPID3 Assessment	X		X	X
Imaging ⁶				
Targeted Therapy Questionnaire	X	X		
RX Adherence Check			X	X
Initiation or Change of Targeted Therapy		X		
Current RA Medications	X	X	X	X
Socioeconomic Status ⁸				X

Abbreviations: CRP (C-Reactive Protein), N/A (Not Applicable), RA (Rheumatoid Arthritis), RF (rheumatoid factor), and RX (Treatment).

Note: At the discretion of the Investigator, pre-screening standard of care lab tests (e.g., CBC, CMP, and/or CRP) may be ordered if patient does not have lab tests within 3 months of Visit 1.

¹ PrismRA results will be provided to the Investigator based on the patient's assigned treatment selection arm. Investigators will receive the test results only for those patients in the informed treatment selection arm.

² Performed via standard lab practices utilizing the same local lab. Visit 1 results can be from a test within 3 months prior to Visit 1.

³ If available, results can be provided from patient's medical records.

⁴ If required by the Investigator, test can either be QuantiFERON Gold TB Test, local PPD TB test, or T-Spot.

⁵ If required by the Investigator, a urine pregnancy test for child-bearing potential females should be completed.

⁶ If available, results for imaging (e.g., X-rays, ultrasound, magnetic resonance imaging, or total sharp score) to be pulled from patient's medical records.

⁷ PrismRA results must be received and reviewed prior to study treatment initiation for the PrismRA arm only.

⁸ Smoking, comorbidities, and socioeconomic status information collected at Visit 4 reflects patient's status at Baseline.

External control arm:

No prospective data collection schedule is enforced, and the data collection is based on routine clinical encounters. Existing data will be mapped from these routine clinical encounters in the following manner.

Data Element	Baseline	Study Treatment Initiation	12 Week Follow-up	Visit 4 (24 Week Follow-up)
Visit Windows	3 months	(Precise index date)	±4 weeks	±4 weeks
Informed Consent	X			
Medical Records Release Form	X			
Eligibility Criteria	X			
RA Medical History	X			
Smoking	X			
Comorbidities	X			
Weight	X		X	X
28 Joint-Count for Tenderness & Swelling	X		X	X
PrismRA ¹	N/A			
CRP	X		X	X
RF	X			
Vectra DA	N/A			
TB Test	N/A			
Urine Pregnancy Test	N/A			
Physician Global Assessment of Disease Activity	X		X	X
Patient Global Assessment of Pain	X		X	X
Patient Global Assessment of Disease Activity	X		X	X
Health Assessment Questionnaire	X		X	X
RAPID3 Assessment	X		X	X
Imaging ⁶	N/A			
Targeted Therapy Questionnaire	N/A			
RX Adherence Check (defined as continuation of the study treatment)			X	X
Initiation or Change of Targeted Therapy		N/A		
Current RA Medications	X		X	X
Socioeconomic Status ¹	X			

Abbreviations: CRP (C-Reactive Protein), N/A (Not Applicable), RA (Rheumatoid Arthritis), RF (rheumatoid factor), and RX (Treatment).

¹ Socioeconomic status information will be available for a subset of patients.

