8.9 Data Collection

PrismRA arm:

Patient data will be collected from clinical assessments, medical records, imaging, laboratory results, and surveys at screening/baseline, treatment initiation and follow-up visits and entered in the study database.

If a completed medical records release form is on file, comprehensive demographic, medical, and health information (if available) may be directly collected from the patient's electronic medical records by the Sponsor. Electronic Medical Records (EMR) data may be obtained indefinitely following a patient's enrollment unless the patient withdraws authorization.

Data from the PrismRA (Visit 1) samples will be stored at Scipher Medicine's Clinical Laboratory Improvement Amendments (CLIA)-certified and College of American Pathologists (CAP)-accredited laboratory.

External control arm:

In the external control arm, the existing data in OM1's PremiOM RA will be utilized. No new data collection will be performed.

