5.4 Handling Missing Data

Missing data will be handled with two approaches: (1) minimizing the chance of missing data in the study design and conduct stages, and (2) handling missing data with statistical methods in the analysis phase.

The following measures will be taken to reduce missing data in the study design.

PrismRA arm: Missing data will be minimized through rigorous conduct of data collection as described in Section 8.9 of the Protocol. See below for the handling of missing follow-up data.

External control arm: At least one observed CDAI measurement in the 3-month period prior to the index date (b/tsDMARD initiation) and at least three observed CDAI measurements in the 12-month period prior to the index date (including the measurements in the aforementioned 3-month period) will be required to ensure patients are selected from practices where CDAI are recorded as a part of routine care.

The following statistical methods will be considered in handling missing data in the analyses.

The rigorous design of the study aims to reduce the amount of missing data in baseline variables. If needed, single imputation [8] of missing baseline characteristics will be used to ensure that all eligible patients are included in the PS model to estimate the probability of treatment [9] for confounding control. Further details of the treatment PS methods are described below in Section 6.3.

Longitudinal outcomes may be unobserved due to patients that are lost-to-follow up ("drop-out"), missed scheduled visits (PrismRA arm), encounters that fall outside of the specified follow up window (external control arm) or not measured during a completed visit. It is anticipated that at 24-weeks roughly 45% of the PrismRA arm and 50% of the external control arm will be missing outcome data. Within each study arm the number and proportion of missing outcomes at

12 and 24-week visits will be described and baseline characteristics of patients with complete versus incomplete outcome data will be compared.

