6.3 Analyses Addressing Primary Study Endpoint

The following statistical approaches apply to all study endpoints outlined in Section 3.

Baseline data analyses. Baseline characteristics and proportion of missing data will be summarized for each study arm. If necessary, single imputation will be used to impute values for missing observations as described in Section 5.4. Covariate balance will be assessed using standardized differences (mean or proportion differences for continuous and binary outcomes, respectively). [17] Balance between study arms will be assessed before and after PS matching.

Propensity score model for the arm assignment. A stratified PS model procedure will be used. Strata will be defined by baseline prior exposure to TNFi treatment (e.g. TNFi-naive and TNFi-exposed). Within unique combinations of subgroup strata logistic regression models will be used to estimate the probability of being assigned to the PrismRA arm using pre-treatment covariates and/or missing data indicator variables. All covariates used to estimate the PS will be measured before initiation of study treatment and are listed in Table 4 of Section 6.2. Inclusion of non-linear terms (e.g., transformations, restricted cubic splines) and variable interactions will be considered on the basis of balance diagnostics and subject matter expertise. The PS model will be fit without using outcome information to avoid selection of a model that leads to a favorable treatment effect estimate. [18] If model convergence issues (e.g. model non-convergence warnings or failures) arise, the PS will be re-estimated using the full eligible cohort. Evaluation of the PS model will rely on the ability of the PS to achieve covariate balance between the PrismRA arm and the external control arm. [19] Covariate balance will be described using standardized differences. Standardized differences greater than 0.1 indicate “meaningful” residual imbalance in the corresponding covariate and indicate the need for further refinement of the PS model. [20] In matched analyses, F tests for equality of variances for continuous variables will be used. [17] Graphical summaries of balance will include boxplots, Love plots [21], and empirical density functions of the distribution of covariates in the PrismRA arm and the external control arm. The distribution and overlap of propensity scores among individuals in the PrismRA arm and the external control arm will be examined graphically.

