Glucocorticoids	Yes	xxx (xx%)	xxx (xx%)	x.xx
	No	xxx (xx%)	xxx (xx%)	

Footnotes

¹ Using all available data before the index date comorbidities are based on the presence of at least two diagnostic codes at least 30 days apart in the external control arm; based on an additional questionnaire in the PrismRA arm.

² Rheumatoid factor or anti-citrullinated peptide antibody.

The following tables will be created using the same layout as Table 1.1.

Table 1.2 Baseline characteristics of modified ITT cohort by study arms after PSM

Table 1.1.1 Baseline characteristics of modified ITT cohort by study arms for TNFi-naïve group before PSM

Table 1.1.2 Baseline characteristics of modified ITT cohort by study arms for TNFi-exposed group before PSM

[figure not shown]
Table 1.2.1 Baseline characteristics of modified ITT cohort by study arms for TNFi-naïve group after PSM

Table 1.2.2 Baseline characteristics of modified ITT cohort by study arms for TNFi-exposed group after PSM

Table 1.3 Baseline characteristics of PrismRA-adherent cohort by study arms before PSM

Table 1.4 Baseline characteristics of PrismRA-adherent cohort by study arms after PSM

Figure 2.1 PS overlap for modified ITT cohort before and after PSM

Programmer note: The figure above is an example figure showing propensity score distributions by study arm before (left panel) and after (right panel) matching.

[figure not shown]
The following figures will be created using the same layout as Figure 2.1.

Figure 2.1.1 PS overlap for modified ITT cohort for TNFi-naïve group before and after PSM

Figure 2.1.2 PS overlap for modified ITT cohort for TNFi-exposed group before and after PSM

Figure 2.2 PS overlap for PrismRA-adherent cohort before and after PSM

Figure 3.1 Baseline covariate balance plots for modified ITT cohort before and after PSM

Programmer note: The figure above is an example figure showing absolute standardized differences before (diamond) and after (circle) matching.

The following figures will be created using the same layout as Figure 3.1.

Figure 3.1.1 Baseline covariate balance plots for modified ITT cohort for TNFi-naïve group before and after PSM

Figure 3.1.2 Baseline covariate balance plots for modified ITT cohort for TNFi-exposed group before and after PSM

Figure 3.2 Baseline covariate balance plots for PrismRA-adherent cohort before and after PSM

Table 2.1 Primary and secondary composite strategy study endpoints for modified ITT cohort by study arm

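### PrismRA-arm smoking and comorbidities are scheduled only at Visit 4, against the SAP rule that propensity-score covariates precede treatment; patients who miss Visit 4 have no named source

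*Protocol*

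**What the plan says.** **PrismRA arm.** In the Protocol 8.6 grid, the smoking and comorbidities rows have a mark under Visit 4 and under no other visit. Footnote 8 adds: "Smoking, comorbidities, and socioeconomic status information collected at Visit 4 reflects patient's status at Baseline". SAP Table 4 names a questionnaire as this arm's source for comorbidities.

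**External control arm.** The companion grid in Protocol 8.6 places both items at Baseline. The footnote to shell Table 1.1 in SAP 10.0 ties control comorbidities to pre-index codes: "Using all available data before the index date comorbidities are based on the presence of at least two diagnostic codes".

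**Propensity score.** SAP 6.3 states: "All covariates used to estimate the PS will be measured before initiation of study treatment", and points to Table 4. That table lists smoking and ten comorbidities and says the RDCI will be derived. SAP 5.5 likewise limits the PS to pre-treatment information, without sight of follow-up.

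**Missing covariates.** Under SAP 5.4, single imputation, if needed, "will be used to ensure that all eligible patients are included in the PS model". SAP 6.3 also allows a PS model "using pre-treatment covariates and/or missing data indicator variables".

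**Other sources.** Protocol 8.9 says: "Patient data will be collected from clinical assessments, medical records, imaging, laboratory results, and surveys at screening/baseline" and at later visits. Direct EMR collection by the sponsor applies "If a completed medical records release form is on file". Protocol 8.2 leaves the request for that form to the investigator's discretion.

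**The concern.** The schedule and the SAP rule cannot both be followed. Footnote 8 makes Baseline the reference period, but the value is still obtained by looking back about 24 weeks after treatment began, and only from patients who attend.

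The comparison is not randomized, so measured balance between the arms carries much of its credibility. In one arm only, whether this block of confounders is observed depends on Week 24 attendance, which is a post-treatment event. For a PrismRA patient who misses Visit 4, the items and the Week 24 outcome are absent together. Balance after matching could then look acceptable because part of it is computed on imputed values, and the plan has no step that separates observed from imputed balance.

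**Working it through.** **1. Timing.** Visit 2 falls 2-6 weeks after Visit 1, and Visit 4 falls 24 ± 2 weeks after Visit 2 (Protocol 8.6).
- From treatment start: 24 - 2 = 22 to 24 + 2 = 26 weeks.
- From Visit 1: 2 + 22 = 24 to 6 + 26 = 32 weeks.

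No value recorded at Visit 4 meets the SAP 6.3 sentence.

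**2. Covariates involved.** Table 4 lists 5 patient characteristics, 1 lifestyle item, 10 comorbidities, 4 RA items and 4 medication items: 5 + 1 + 10 + 4 + 4 = 24. Affected are 1 + 10 = 11 of 24, or 12 of 25 counting the RDCI. Baseline CDAI, prior TNFi use (also the matching stratum), RA duration, serostatus and RA medications are not affected.

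**3. The plan's own power figure.** Evaluable numbers are 600 × 0.55 = 330 and 1,500 × 0.50 = 750. Exact power of the two-sided Fisher test for 40% vs 30% at alpha 0.05 is 88.4%; the plan states 88%. It reproduces. The calculation uses no covariates, so this point does not change it.

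**4. How many patients.** The documents give no rate of missed Visit 4. Anyone who misses it also lacks a Week 24 CDAI, so the planning attrition in SAP Table 1 serves as a ceiling:

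| Missing Week 24 CDAI | Patients of 600 without a scheduled record |
|---|---|
| 30% | 0.30 × 600 = 180 |
| 35% | 0.35 × 600 = 210 |
| 40% | 0.40 × 600 = 240 |
| 45% | 0.45 × 600 = 270 |

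The true number is lower where CDAI is missing at an attended visit, where treatment never starts (outside the modified ITT population), or where sites retrieve the items from records.

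**5. What happens to these patients under the plan.**
- *Matching and balance.* Their values come from one single imputation (SAP 5.4; SAP 6.3.1, step 1). Neither place says whether it is done within arm or across arms. Arm-separate models are specified only for the outcome imputation. Imputing across arms would draw the filled values towards the control arm, whose comorbidities come from codes rather than a questionnaire.
- *Outcome imputation.* Those models include all Table 4 covariates, but for these patients the items are filled in and add no observed information about Week 24.
- *Completeness check.* SAP 5.4 promises that "baseline characteristics of patients with complete versus incomplete outcome data will be compared". For patients incomplete because they missed Visit 4, there is nothing observed to compare on these items.
- *Missing-data indicators.* In the PrismRA arm, an indicator for these items would largely encode Visit 4 attendance and so bring follow-up information into the PS.

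**The case against.** The plan partly covers this. Footnote 8 fixes the reference period, so a reader who infers that the PS would be built on post-treatment health status goes too far. Table 4 covariates are candidates to be considered. Missing covariates have a rule, and the smoking row of shell Table 1.1 allows an unknown category. Medical records are a general collection source. All of that stands, and it rules out saying there is no source at all. What remains is that no section designates records, chart review or medical history for these items, and the Visit 1 history row is specific to RA.

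A reader might also infer a definite bias in the primary difference, by multiplying the missing fraction by a prevalence gap between attenders and non-attenders and by an effect on response. The documents give neither the gap nor the effect. The product also assumes that non-attenders' true Week 24 outcomes enter the analysis. Under SAP 5.4 and 6.3.1 those outcomes are imputed from models containing the same filled covariates, so much of the error may cancel.

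A reader might likewise infer a loss of power at 330 vs 750. Those 330 are the Week 24 completers, who had their scheduled occasion to give these items.

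Nor is the completeness check useless. It also covers Week 12, and patients who missed Week 12 but attended Visit 4, or attended Visit 4 without a CDAI, contribute observed values. It is limited rather than impossible.

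**Conclusion.** The inconsistency between Protocol 8.6 and SAP 6.3 is plain in the text and should be fixed. It affects 11 listed covariates plus the RDCI, in the PrismRA arm only. At most about 180-270 of 600 enrollees would have no named source, taking missing Week 24 CDAI at the planning rates as a proxy for a missed Visit 4; the actual number is not given and is probably lower.

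For those patients, balance rests on an imputation of unstated scope, the outcome imputation gains nothing observed from these items, and the planned comparison has little ability to show differences in them. Whether the primary result is biased, in which direction and by how much, cannot be derived from the documents; the effect may be small. Confidence is high on the inconsistency and the missing source, not on any consequence for the estimate.

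**What to change.** 1. **Protocol 8.6.** Record smoking and comorbidities at Visit 1 for new enrollees. For patients already enrolled, take Baseline status from site medical records dated before the index date or, failing that, by recall at the next contact, noting date and source. Name this as the source when Visit 4 is missed.
2. **SAP 6.3.** Reword the timing sentence so that it is true for patients already enrolled: covariates describe pre-treatment status, and those recorded later are listed. Without this, recall at a later contact would still break the rule. Do not use missing-data indicators for items whose missingness depends on Visit 4 attendance.
3. **SAP 5.4.** State whether the single imputation of these items is within arm or pooled.
4. **Reporting.** Give missingness of these items by arm and by Visit 4 attendance. Show standardized differences on observed values beside those on imputed values. Add one sensitivity analysis that omits these items from the PS.

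Socioeconomic status can stay at Visit 4, since SAP 6.2 uses it only descriptively.

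**Cost.** A CRF and schedule amendment with IRB handling, some records work and one extra analysis; no added visits or patients. Two limits remain. Protocol 11.1 dates enrollment from March 2022, so Visit 1 will have passed for some patients, and the documents do not say how many. The questionnaire-versus-code difference between arms persists whichever visit is used.
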